12.0 Descriptive Factors

12.1 BRAF analysis done: Yes vs. no.

12.11 If yes, wild-type vs. mutated.

12.2 KRAS analysis done: Yes vs. no.

12.21 If yes, wild-type vs. mutated.

12.3 ECOG Performance Status: 0 vs. 1.

12.4 Age: <70 vs. ≥70.

13.0 Treatment/Follow-up Decision at Evaluation of Patient

- 13.1 A patient is deemed *ineligible* if after registration, it is determined that at the time of registration, the patient did not satisfy each and every eligibility criteria for study entry. The patient may continue treatment off-protocol at the discretion of the physician as long as there are no safety concerns, and the patient was properly registered. The patient will go directly to the event-monitoring phase of the study (or off study, if applicable).
- If the patient received treatment, all data up until the point of confirmation of ineligibility must be submitted. Event monitoring will be required per Section 18.0 of the protocol.
 - If the patient never received treatment, on-study material must be submitted. Event monitoring will be required per Section 18.0 of the protocol.
- 13.2 A patient is deemed a major violation, if protocol requirements regarding treatment in cycle 1 of the initial therapy are so severely violated that evaluability for the primary endpoint is questionable. All data up until the point of confirmation of a major violation must be submitted. The patient will go directly to the event-monitoring phase of the study. The patient may continue treatment off-protocol at the discretion of the physician as long as there are no safety concerns, and the patient was properly registered. Event monitoring will be required per Section 18.0 of the protocol.
- 13.3 A patient is deemed a cancel if he/she is removed from the study for any reason before any study treatment is given. On-study material and the End of Active Treatment/Cancel Notification Form must be submitted. No further data submission is necessary.
- 13.4 Patients will continue treatment until progression, unacceptable adverse events, or patient refusal. Treatment will then be discontinued and the patient will go to event monitoring and be followed per Section 18.0.
- 13.5 Patients who are CR, PR, or SD will continue treatment per protocol.
- 13.6 Patients who develop PD while receiving therapy will go to the event-monitoring phase.
- 13.7 Patients who go off protocol treatment for reasons other than PD will go to the event-monitoring phase per Section 18.0.

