6.12 Correlative Research

- A mandatory correlative research component is part of this study. The patient will be automatically registered onto this component (see Sections 3.0 and 14.0).
- A mandatory banking component is part of this study. The patient will be automatically registered onto this component (see Sections 3.0 and 14.0).

- 6.13 Documentation of IRB approval must be on file in the Registration Office before an investigator may register any patients.

In addition to submitting initial IRB approval documents, ongoing IRB approval documentation must be on file (no less than annually) at the Registration Office ([REDACTED]). If the necessary documentation is not submitted in advance of attempting patient registration, the registration will not be accepted and the patient may not be enrolled in the protocol until the situation is resolved.

When the study has been permanently closed to patient enrollment, submission of annual IRB approvals to the Registration Office is no longer necessary.

- 6.14 Prior to accepting the registration/randomization, the registration/randomization application will verify the following:
- IRB approval at the registering institution
 - Patient eligibility
 - Existence of a signed consent form
 - Existence of a signed authorization for use and disclosure of protected health information
- 6.15 At the time of randomization, the following will be recorded:
- Patient has given permission for ACCRU to give his/her sample(s) to outside researchers.
- 6.16 Treatment cannot begin prior to randomization and must begin ≤ 7 days after randomization.
- 6.17 Pretreatment tests/procedures (see Section 4.0) must be completed within the guidelines specified on the test schedule.
- 6.18 All required baseline symptoms (see Section 10.5) must be documented and graded.
- 6.19a Treatment on this protocol must commence at an ACCRU institution under the supervision of a medical oncologist.
- 6.19b Blood draw kit is available on site.
- 6.19c Patient questionnaire booklet is available on site; copies are not acceptable for this submission.
- 6.2 Randomization Procedures
- 6.21 The registering membership will be used as the only stratification factor for this study.

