16.4 Supplementary Analysis Plans (includes all secondary and translational goals)

- 16.41 Overall survival (OS) is defined as time from randomization to death due to any cause. OS will be estimated with Kaplan-Meier survival curves and differences between regorafenib arms (A vs. B) tested using log-rank tests, though we note these analyses are not powered for formal non-inferiority assessments. See Section 2.21.
- 16.42 Progression-free survival (PFS) is defined as the time from randomization to the earlier of disease progression or death due to any cause, where progressed disease (PD) is as defined by RECIST 1.1 (see Section 11.0). PFS will be estimated with Kaplan-Meier survival curves and differences between regorafenib arms (A vs. B) tested using log-rank tests, though we note these analyses are not powered for formal non-inferiority assessments. See Section 2.21.
- 16.43 Time to progression (TTP) is defined as the time from randomization to disease progression, where progressed disease (PD) is defined by RECIST 1.1 (see Section 11.0). TTP will be estimated with Kaplan-Meier survival curves and differences between regorafenib arms (A vs. B) tested using log-rank tests, though we note these analyses are not powered for formal non-inferiority assessments. See Section 2.21.
- 16.44 The cumulative (total) dose of regorafenib received by patients and dose intensity in the first two cycles will be summarized with descriptive statistics and compared between regorafenib arms (A vs. B) using the t-test (if approximately normally distributed) or the Wilcoxon rank sum test (if not approximately normally distributed). Dose intensity is defined as the cumulative (total) dose of regorafenib divided by the expected total dose. See Section 2.22.
- 16.45 The proportion of patients overall and within each arm experiencing grade 3 or 4 HFS or fatigue will be computed with 95% confidence intervals, and differences between regorafenib dosing strategies (pooled across HFS strategies) tested using a Fisher Exact test. The incidence of grade 3 or 4 HFS will also be descriptively compared between those receiving a pre-specified preemptive vs. reactive approach for hand and foot syndrome (pooled across dosing strategies), and tested using a Fisher Exact test. See Section 2.24. Adverse event reports will be shared with [name] of Memorial Sloan Kettering Cancer Center 1-2 times per month for review.

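### Randomised patients who cancel before the first dose are not followed, so OS, PFS and TTP are not strictly compared in the groups as randomised

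*Combined protocol and SAP*

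**What the plan says.** Section 13.3 defines the category: "A patient is deemed a cancel if he/she is removed from the study for any reason before any study treatment is given". The site sends the on-study material and the cancel notification form, after which "No further data submission is necessary".

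Cancels arise after allocation, because Section 6.16 states: "Treatment cannot begin prior to randomization and must begin ≤ 7 days after randomization".

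Section 13.1 treats never-treated ineligible patients differently: "If the patient never received treatment, on-study material must be submitted. Event monitoring will be required per Section 18.0 of the protocol". Its opening paragraph adds that such a patient may go off study instead where that applies. Sections 13.2, 13.4, 13.6 and 13.7 send major violations, patients stopping for progression, toxicity or refusal, and other patients off treatment to event monitoring.

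In the analysis plan, Section 16.41 says "Overall survival (OS) is defined as time from randomization to death due to any cause" and Section 16.42 says "Progression-free survival (PFS) is defined as the time from randomization to the earlier of disease progression or death due to any cause". TTP (16.43) has the same origin. Each is tested A versus B by log-rank, "though we note these analyses are not powered for formal non-inferiority assessments". No analysis population is named for these endpoints. The evaluable set in Section 16.3 (eligible, consented, treated) is defined for the primary endpoint. Section 16.8 excludes patients with missing data from the relevant analyses, without imputation.

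**The concern.** A log-rank test of A versus B from randomisation is protected by randomisation only if everyone randomised contributes. Here a group defined by something that happens after allocation contributes nothing.

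The arms differ visibly in starting dose (80 mg or 160 mg daily) and in cream strategy (pre-emptive or reactive), and no blinding or placebo is described. A patient or site could therefore withdraw because of the allocation. Rapid decline in the days before the first dose could also cause cancellation, which would make cancels a poor-prognosis group. If cancels are unevenly spread and do worse, omitting them flatters the arm that has more of them.

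Section 1.1 states the aim of keeping the observed benefit while improving tolerability, and Section 2.21 makes PFS, TTP and OS the efficacy goals. The planned between-arm survival comparison should therefore rest on the randomised groups where that is cheap to achieve.

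**Working it through.** **1. The plan's own figures.** Inputs from Section 16.3: 45% versus 63%, one-sided alpha 0.20, 80% power, Fisher exact test. Exact enumeration gives power 79.7% at 54 per arm and 80.4% at 55 per arm, so 110 evaluable patients reproduces. Inflating by 10% gives 110 / (1 − 0.10) = 122.2, rounded up to 123. The sample size is not in dispute; it shows only what losses were planned for.

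**2. How many patients could be affected.** The allowance is 123 − 110 = 13, and 13 / 123 = 10.6%. Section 16.3 shares it among ineligibility, cancellation, major treatment violation and other reasons. It is a planning figure, not a cap, and the number of cancels is not given.

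**3. What happens to a cancel in the analysis.** With no follow-up, a cancel is either excluded under 16.8 or censored at about day 0. The plan does not say which. Neither adds anything to a log-rank test, so the result is the same. The data forms in Section 18.1 do not override 13.3: before therapy starts they add only an Off Treatment form for withdrawal or refusal.

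**4. Size, by illustration.** All values in this step are assumed except the total of 123, split 61 (B) and 62 (A). Let six-month survival be 50% in treated patients of both arms and 30% in cancels.

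- 6 cancels in B, 2 in A: B = (55 × 0.5 + 6 × 0.3) / 61 = 48.0%; A = (60 × 0.5 + 2 × 0.3) / 62 = 49.4%. The difference is 1.3 points before rounding, where the treated-only comparison shows zero.
- 9 in B, 4 in A (the whole allowance taken as cancels): B = (52 × 0.5 + 9 × 0.3) / 61 = 47.0%; A = (58 × 0.5 + 4 × 0.3) / 62 = 48.7%. The difference is 1.7 points.

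The standard error of the A−B difference at 50% survival is √(0.25/61 + 0.25/62) = 0.090. The hidden difference is thus 0.013 / 0.090 ≈ 0.15 to 0.017 / 0.090 ≈ 0.18 standard errors.

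**5. A more extreme assumed case.** Put all k cancels in one arm of 62, with exponential survival, a treated median of 7.0 months and a cancel median m of 2 to 4 months. With w = k/62, solve (1 − w) × 0.5^(t/7) + w × 0.5^(t/m) = 0.5 for the as-randomised median t.

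| Cancels, all in one arm | As-randomised median (months) | Median if cancels omitted |
|---|---|---|
| 3 | 6.6–6.8 | 7.0 |
| 6 | 6.2–6.6 | 7.0 |
| 9 | 5.8–6.4 | 7.0 |
| 13 | 5.3–6.2 | 7.0 |

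The last row needs every allowed loss to be a cancel and all of them in the same arm.

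**The case against.** The best case for leaving the plan alone is that the effect is small and falls on secondary endpoints in a phase II trial tested at one-sided 0.20. OS, PFS and TTP are declared unpowered, and the primary endpoint is defined among treated patients, so it is untouched. The illustrated bias is under a fifth of a standard error and depends on an imbalance and a survival deficit that the documents do not supply. All of this stands, and it limits the weight of the point.

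The remedy also has limits. A patient who leaves on learning the allocation may refuse follow-up as well, and Section 18.1 provides a form for withdrawing from all follow-up. Event-monitoring status forms are due every six months until progression, whereas scans in active monitoring are every eight weeks. Progression times in cancels would be ascertained differently. That stands too: the gain is clear for OS and doubtful for PFS and TTP.

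A reader might infer that the plan chooses to follow ineligible patients and drop eligible ones. The documents do not support a reading that clean. Section 13.1 allows going off study where applicable, and an ineligible patient removed before dosing meets both 13.1 and 13.3. The rules overlap and need reconciling.

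A reader might also infer that survival is the only evidence that benefit is maintained. It is not. Treatment stops at progression and tumours are measured in cycle 2, so starting cycle 3 partly reflects freedom from early progression. Goal 2.32 also looks at response or stable disease after two cycles, in relation to PK.

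**Conclusion.** The point holds as a modest, inexpensive improvement. As written, the plan gives a comparison of OS, PFS and TTP that is not strictly of the groups as randomised once any patient cancels, and Sections 16.2 and 16.3 expect cancellations. The likely effect is small: 1.3 to 1.7 percentage points of six-month survival under the assumed values, and more only if cancels are numerous and concentrated in one arm. Neither size nor direction can be fixed from the documents.

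The argument that cancellation could depend on arm rests on an inference that allocation is known, because no blinding is described; the documents do not use the term open-label. It would also go too far to call the loss irreparable. Section 13.3 says further data are not needed; it does not forbid collecting them. Following the plan as written would nevertheless leave these patients without outcome data. The sample sizes of 110 and 123 and the primary analysis are unaffected.

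**What to change.** - Amend 13.3 so that cancels go to event monitoring per Section 18.0 unless they withdraw consent to all follow-up.
- Reconcile 13.3 with 13.1, so that an ineligible patient removed before dosing falls under one rule.
- State in 16.41 that OS includes all randomised patients by assigned arm.
- In 16.42 and 16.43, analyse PFS and TTP by assigned arm as well, noting that progression in cancels is ascertained only six-monthly.
- Tabulate cancels and their reasons by arm. The forms already required should largely supply this.

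The cost is a sentence or two in Section 13, wording in 16.41 to 16.43, and existing status forms for a few patients. With follow-up ending two years after registration, six-monthly reporting means at most 24 / 6 = 4 scheduled forms per patient, plus event forms. Some cancels will refuse follow-up, so the repair will be partial.

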4.0 Test Schedule

Tests and procedures	Active Monitoring Phase										
	≤7 days prior to randomization	Cycle 1 ¹³				Cycle 2 ¹³				After week 8: Every 4 weeks until progression (+/- 3 days)	At PD, withdrawal or removal
		Week 1 (Day 1)	Week 2 (Day 8)	Week 3 (Day 15)	Week 4 (Day 22)	Week 1 (Day 1)	Week 2 (Day 8)	Week 3 (Day 15)	Week 4 (Day 22)		
History and exam, weight, ECOG PS ¹² , blood pressure	X	X ¹²	X	X	X	X	X	X	X	X	X
Height	X										
Adverse event assessment ⁸	X		X	X	X	X	X	X	X	X	X
Hematology ^{8, 11} : CBC/ differential, ANC, INR/PTT ^{8, 10}	X	X				X				X	
Chemistry ^{8, 11} : SGOT (AST), alk phos, T. bili, serum creatinine, calcium, glucose, Na, K, SGPT (ALT)	X	X		X ⁷		X ⁷		X ⁷		X	
Albumin	X										
Urine proteinuria or urine protein creatinine ratio	X										
Tumor measurement ⁸ (CT scan of chest, abdomen and pelvis) (MRI if CT is not feasible)	X ¹								X ¹	X ¹	X ^{1,9}
ECG ⁶	X										
Serum pregnancy test	X ²										
Mandatory blood sample (see Section 14.0)	X ^{4,R}	(Day 7) X ^{4,R}	(Day 14) X ^{4,R}	(Day 21) X ^{4,R}		(Day 1) X ^{4,R}		(Day 21) X ^{4,R}			
Patient Medication Diary (Appendix II) ³		X	X	X	X	X	X	X	X	X	
Patient Questionnaire Booklets (Appendices IV, V, VI)	X ⁵		X ^{5,8}			X ^{5,8}	X ^{5,8}		X ^{5,8}		

1. CT scans preferred (MRI if CT is not feasible) of the chest, abdomen and pelvis. Use same imaging throughout the study. Tumor measurements at baseline (≤28 days prior to randomization) and every 8 weeks until progression.
2. For women of childbearing potential only.

3. The diary must begin the day the patient starts taking the medication and must be completed per protocol and returned to the treating institution weekly during Cycles 1 and 2 and every 4 weeks thereafter.
 4. Kits are required for this collection. Samples will be collected for PK analysis of C_{min} of regorafenib, M2 and M5 at the following time points: Cycle 1, days 7, 14 and 21 prior to treatment; Cycle 2, days 1 and 21, prior to treatment. Samples will be collected for research banking at the following time points: Baseline, prior to treatment; Cycle 2, days 1 and 21, prior to treatment. See Section 14.0 for specific instructions.

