8.1 Arm A Regorafenib Dose Escalation/Reduction

Dose level	If No SDRT	If + SDRT**
80 mg*	Proceed to next dose level	-
120 mg	Proceed to next dose level	Decrease to 80 mg
160 mg	-	Decrease to 120 mg

*starting dose level

**SDRT = Significant Drug Related Toxicities

- 8.11 After week 8, if toxicities have resolved to \leq Grade 0-1, re-escalation is allowed 40 mg at a time every 4 weeks to a maximum of 160 mg and at the discretion of the treating investigator.
- 8.12 Patients with dose reductions below 80 mg should go off treatment and go to event monitoring.
- 8.13 Any patients with toxicities requiring >4 week delay should go off treatment and then to event monitoring.

Regorafenib may be dose reduced per the table in Section 8.2 in case of intolerable toxicity such as weight loss, fatigue, rash or anorexia.

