8.3 Regorafenib Dose Modifications

Table 8.31 Recommended dose modification for toxicities except hand-foot-skin reaction, hypertension and ALT/AST/bilirubin			
NCI-CTCAE v4.0^a	Dose Interruption	Dose Modification^b	Dose for Subsequent Cycles
Grade 0-2	Treat on time	No change	
Grade 3	Delay until \leq Grade 2 ^c	Reduce by 1 dose level	If toxicity remains < Grade 2, dose re-escalation can be considered at the discretion of the treating investigator. If dose is re-escalated and toxicity (\geq Grade 3) recurs, institute permanent dose reduction.
Grade 4	Delay until \leq Grade 2 ^c	Reduce by 1 dose level. Permanent discontinuation can be considered at treating investigator's discretion.	
a. NCI-CTCAE = National Cancer Institute - Common Terminology Criteria for Adverse Events, version 4.0 b. Excludes alopecia, non-refractory nausea/vomiting, lymphocyte count decreased, non-refractory hypersensitivity and nonclinical and asymptomatic laboratory abnormalities. c. If no recovery after a 4 week delay*, treatment should be permanently discontinued unless subject is deriving clinical benefit. * Modify according to study specific cycle length			

If greater than 2 dose level reductions are required, regorafenib will be discontinued and the rest of the study follow up may be continued. The following tables outline dose adjustments for toxicities related to regorafenib except hand-foot skin reaction, hypertension and liver function test abnormalities.

The table above outlines dose adjustments for hematologic and non-hematologic toxicities related to regorafenib except PPES and hypertension. In addition to these recommended dose modifications, subjects who develop diarrhea, mucositis, anorexia or other events predisposing to fluid loss or inadequate fluid intake should be carefully monitored and rehydrated as clinically necessary. This is in order to minimize the risk of postural hypotension and renal failure.

	Grade 1	Grade 2	Grade 3
NCI-CTCAE v4.0 Palmar-plantar erythrodysesthesia syndrome	Minimal skin changes or dermatitis (e.g., erythema, edema, or hyperkeratosis) without pain	Skin changes (e.g., peeling, blisters, bleeding, edema, or hyperkeratosis) with pain	Severe skin changes (e.g., peeling, blisters, bleeding, edema, or hyperkeratosis) with pain

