11.0 Treatment Evaluation Using RECIST Guideline

NOTE: This study uses protocol RECIST v1.1 template dated 2/16/2011. See the footnote for the table regarding measurable disease in Section 11.44, as it pertains to data collection and analysis.

Response and progression will be evaluated in this study using the new international criteria proposed by the revised Response Evaluation Criteria in Solid Tumors (RECIST) guidelines (version 1.1) (Eisenhauer et al., 2009). Changes in the largest diameter (unidimensional measurement) of the tumor lesions and the short axis measurements in the case of lymph nodes are used in the RECIST guideline.

- 11.1 Schedule of Evaluations: For the purposes of this study, patients should be reevaluated every 8 weeks.
- 11.2 Definitions of Measurable and Non-Measurable Disease
- 11.21 Measurable Disease
- 11.211 A non-nodal lesion is considered measurable if its longest diameter can be accurately measured as ≥ 2.0 cm with chest x-ray, or as ≥ 1.0 cm with CT scan, CT component of a PET/CT, or MRI.
- 11.212 A superficial non-nodal lesion is measurable if its longest diameter is ≥ 1.0 cm in diameter as assessed using calipers (e.g. skin nodules) or imaging. In the case of skin lesions, documentation by color photography, including a ruler to estimate the size of the lesion, is recommended.
- 11.213 A malignant lymph node is considered measurable if its short axis is ≥ 1.5 cm when assessed by CT scan (CT scan slice thickness recommended to be no greater than 5 mm).
- 11.22 Non-Measurable Disease
- 11.221 All other lesions (or sites of disease) are considered non-measurable disease, including pathological nodes (those with a short axis ≥ 1.0 to < 1.5 cm). Bone lesions, leptomeningeal disease, ascites, pleural/pericardial effusions, lymphangitis cutis/pulmonis, inflammatory breast disease, and abdominal masses (not followed by CT or MRI), are considered as non-measurable as well.
- Note: ‘Cystic lesions’ thought to represent cystic metastases can be considered as measurable lesions, if they meet the definition of measurability described above. However, if non-cystic lesions are present in the same patient, these are preferred for selection as target lesions. In addition, lymph nodes that have a short axis < 1.0 cm are considered non pathological (i.e., normal) and should not be recorded or followed.
- 11.3 Guidelines for Evaluation of Measurable Disease
- 11.31 Measurement Methods:

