11.44 Overall Objective Status

The overall objective status for an evaluation is determined by combining the patient's status on target lesions, target lymph nodes, non-target lesions, non-target lymph nodes, and new disease as defined in the following tables:

For Patients with Measurable Disease

Target Lesions & Target Lymph Nodes	Non-Target Lesions & Non-Target Lymph Nodes	New Sites of Disease	Overall Objective Status
CR	CR	No	CR
CR	Non-CR/Non-PD	No	PR
PR	CR Non-CR/Non-PD	No	PR
CR/PR	Not All Evaluated*	No	PR**
SD	CR Non-CR/Non-PD Not All Evaluated*	No	SD
Not all Evaluated	CR Non-CR/Non-PD Not All Evaluated*	No	Not Evaluated (NE)
PD	Unequivocal PD CR Non-CR/Non-PD Not All Evaluated*	Yes or No	PD

Target Lesions & Target Lymph Nodes	Non-Target Lesions & Non-Target Lymph Nodes	New Sites of Disease	Overall Objective Status
CR/PR/SD/PD/Not all Evaluated	Unequivocal PD	Yes or No	PD
CR/PR/SD/PD/Not all Evaluated	CR Non-CR/Non-PD Not All Evaluated*	Yes	PD

*See Section 11.431

** NOTE: This study uses the protocol RECIST v1.1 template dated 2/16/2011. For data collection and analysis purposes the objective status changed from SD to PR in the ACCRU protocol RECIST v1.1 template as of 2/16/2011 and to match RECIST v1.1 requirements.

For Patients with Non-Measurable Disease Only:

Non-Target Lesions & Non-Target Lymph Nodes	New Sites of Disease	Overall Objective Status
CR	No	CR
Non-CR/Non-PD	No	Non-CR/Non-PD
Not All Evaluated*	No	Not Evaluated (NE)
Unequivocal PD	Yes or No	PD
Any	Yes	PD

*See Section 11.431

11.45 Symptomatic Deterioration: Patients with global deterioration of health status requiring discontinuation of treatment without objective evidence of disease progression at that time, and not either related to study treatment or other medical conditions, should be reported as PD due to “symptomatic deterioration.” Every effort should be made to document the objective progression even after discontinuation of treatment due to symptomatic deterioration. A patient is classified as having PD due to “symptomatic deterioration” if any of the following occur that are not either related to study treatment or other medical conditions:

- Weight loss >10% of body weight.
- Worsening of tumor-related symptoms.
- Decline in performance status of >1 level on ECOG scale.

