CRF	Event Monitoring Phase ¹				
	q. 6 months until PD	At PD	After PD q. 6 mos.	Death	At Each Event Occurrence
Patient Status: Survival and Disease Status Follow-Up/Event Monitoring	X ²	X ²	X	X	At each occurrence
Adverse Events: Late ³					At each occurrence
Lost to Follow-Up ³					At each occurrence
Notice of New Primary ³					At each occurrence
First Non-Protocol Treatment ⁴					At each occurrence
Consent Withdrawal (choose appropriate form) ³ 
 • Consent Withdrawal: QOL Only • Consent Withdrawal: Specimen Only • Consent Withdrawal: All Follow-Up 					At each occurrence

1. If a patient is still alive 2 years after registration, no further follow-up is required.
2. Attach a copy of documentation of response or progression in RAVE on the Supporting Documentation Form.
3. Submit only if applicable.
4. Please use the “Add Event” function to record the first instance of non-protocol treatment received. If the patient has never had any non-protocol treatment, record as “no” at the end of the Event Monitoring Phase.

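### The documents conflict on whether 8-weekly tumour assessment continues after a treatment stop without progression, which could modestly bias the secondary PFS and TTP comparisons

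*Combined protocol and SAP*

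**What the plan says.** Two sets of statements bear on tumour assessment after a patient stops regorafenib without progression.

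**Towards continued 8-weekly assessment**
- Section 4.0, footnote 1: "Tumor measurements at baseline (≤28 days prior to randomization) and every 8 weeks until progression". The endpoint named is progression, not end of treatment.
- Section 11.1: "For the purposes of this study, patients should be reevaluated every 8 weeks". Treatment status is not mentioned.

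**Towards event monitoring without scheduled scans**
- Section 13.7: "Patients who go off protocol treatment for reasons other than PD will go to the event-monitoring phase per Section 18.0".
- Section 13.4, covering stops for adverse events or refusal as well as progression: "Treatment will then be discontinued and the patient will go to event monitoring and be followed per Section 18.0".
- Section 8.12 (repeated for Arm B in 8.22): "Patients with dose reductions below 80 mg should go off treatment and go to event monitoring". Section 8.13 does the same for long toxicity delays.
- Section 18.1, follow-up table: the status form is due "q. 6 months until PD", with a further form at PD. No tumour measurement form or imaging is listed.
- The grid to which footnote 1 belongs is headed Active Monitoring Phase, and eligibility item 3.19c ties the commitment to return to the enrolling site to that phase.

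The text under Table 8.31 leaves the matter open: after more than two dose level reductions, "regorafenib will be discontinued and the rest of the study follow up may be continued".

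Sections 16.42 and 16.43 compare PFS and TTP between pooled Arms A and B by log-rank test, with PD defined by RECIST 1.1 and a pointer to Section 11.0. Section 11.0 also contains 11.45, under which some patients are recorded as PD "without objective evidence of disease progression at that time". No censoring rule is given for patients who stop without PD; Section 16.8 only excludes patients with missing data.

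**The concern.** If the interval at which progression can be found depends on whether a patient is still on treatment, and the arms differ in how often patients stop for toxicity, measured PFS and TTP differ between arms even when true progression times do not. The background and Section 16.3 attribute early discontinuation largely to adverse events, and the dose-escalation strategy is meant to reduce it. If the strategy works, Arm B has more non-PD stops, its progressions are dated later, and Arm A looks worse than it is. Section 1.1 aims to keep the observed benefit while improving tolerability, so readers will look at these curves for reassurance. Scans that were never taken cannot be recovered at analysis.

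**Working it through.** **The plan's own figure.** The documents give no event count, hazard ratio or power for PFS or TTP. The only sample-size figure is for the primary endpoint (45% vs 63%, one-sided alpha 0.20, power 80%, N = 110). It reproduces: exact Fisher power at 55 per arm is 0.804, and the continuity-corrected formula gives 54 per arm, 108 in total. The present point does not turn on it.

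**Detection lag on the literal reading.** Let T be true progression and S the week of a toxicity stop, with S < T.
- 8-weekly scanning: detected at 8 × ceil(T/8), a lag of at most 8 weeks.
- Detection only at 26-week contacts from the stop: S + 26 × ceil((T − S)/26), a lag of at most 26 weeks.

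Example: S = 4 and T = 10. With 8-weekly scans PD is dated at week 16 (lag 6). With 26-weekly contact it is dated at week 4 + 26 = 30 (lag 20), unless death comes first.

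**Simulation with no true A vs B difference.** From the documents: the 8-week and 6-month intervals, 1:1 pooled allocation, 55 per arm, follow-up capped at 2 years (104 weeks). Assumed, because the documents give no values: exponential time to PD with median 2, 3 or 4 months; median PD to death 4 months; toxicity stops only in weeks 1 to 8, at the rates shown. Observed PFS is the earlier of detected PD and death. The hazard ratio is the one-step log-rank estimate, exp[(O − E)/V], from 200,000 patients per arm.

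| Median time to PD | Stops A / B | HR (A/B), 8-weekly throughout | HR (A/B), 26-weekly after a stop |
|---|---|---|---|
| 2 months | 10% / 10% | 1.002 | 1.002 |
| 2 months | 10% / 25% | 1.002 | 1.064 |
| 2 months | 5% / 30% | 0.994 | 1.107 |
| 3 months | 10% / 10% | 1.007 | 1.001 |
| 3 months | 10% / 25% | 1.000 | 1.044 |
| 3 months | 5% / 30% | 1.003 | 1.073 |
| 4 months | 10% / 10% | 0.996 | 1.002 |
| 4 months | 10% / 25% | 1.005 | 1.031 |
| 4 months | 5% / 30% | 1.007 | 1.051 |

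Over a wider set of assumptions (Arm B 10 to 30 points higher, medians of about 9 to 17 weeks), the null hazard ratio under 26-weekly detection is about 1.01 to 1.12.

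**Effect on the test.** With 55 per arm, the two-sided 5% log-rank test rejects in 4.6% to 5.7% of null trials under 8-weekly scanning. Under 26-weekly detection with unequal stops it rejects in 5.1% to 7.6%.

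**Against the precision available.** With about 105 events (an assumption), the 95% limits on a hazard ratio are a factor of exp(1.96 × 2/√105) = 1.47 either way. A shift of 1.01 to 1.12 is small beside that, but it is systematic.

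**The case against.** **The documents do not clearly end 8-weekly scanning.** A reader might infer from 13.7 that patients who stop early definitely leave the scan schedule. Footnote 1 and Section 11.1 say otherwise, so what is shown is a conflict, not a settled switch. This objection stands and sets the limit of the point.

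**Six months is a reporting interval, not a scan interval.** The 18.1 table has a column for PD itself, with documentation attached, so progression found in usual care is reported when it happens. The Section 4.0 grid also marks a tumour measurement at withdrawal or removal. Both stand, and they make 26-weekly detection a worst case. But a scan at withdrawal cannot date later progression, and usual care is not a common schedule. The first 6-monthly form also falls at about the end of the roughly 6 months of follow-up planned in Section 16.2.

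**Unequal stop rates are assumed.** This stands. The 45% and 63% in Section 16.3 are completion rates that include progression, not toxicity-stop rates. With equal rates the bias vanishes.

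**Two stronger readings are not supported.**
- A reader might express the bias as a gap of several weeks in median PFS. In the simulation the two medians differ by 0.9 weeks (16.0 vs 16.9) and 3.8 weeks (16.0 vs 19.8) at a 3-month true median, but by 0 to 0.4 weeks at 2 and 4 months. The larger gap arises where the 50% point lies next to a jump between scan dates, so it is not a fair summary.
- A reader might infer that drug-induced weight loss is counted as progression under 11.45. That section twice excludes deterioration related to study treatment and asks for objective progression to be documented afterwards. What remains is only that attribution is judged open-label.

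**Conclusion.** The conflict between footnote 1 and Section 11.1 on one side, and Sections 13.4, 13.7 and 18.1 on the other, is real and should be reconciled. The bias is conditional: it needs sites to follow the event-monitoring text literally and Arm B to have more non-PD stops. Under those conditions it runs against Arm A and is modest, with a null hazard ratio (A/B) of about 1.01 to 1.12 as an upper scenario. The size rests on stop rates and progression and survival medians that the documents do not give. It also depends on an unstated censoring choice: censoring non-PD stoppers at their last scan would replace late detection with possible informative censoring.

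A reader might take this as undermining the trial's main conclusion. It does not. Sections 16.41 to 16.43 say the survival analyses are not powered for non-inferiority, and neither the primary endpoint nor OS depends on scan timing after a stop.

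**What to change.** 1. State in Section 13.7 (and 13.4) that patients who stop without PD continue tumour assessment every 8 weeks until PD or death, consistent with footnote 1 and Section 11.1. Add the matching row and forms to the Section 18.1 follow-up table, and align the sentence under Table 8.31.
2. Add a PFS and TTP censoring rule covering patients who stop without PD and those who miss assessments.
3. Add a PFS and TTP sensitivity analysis that counts only objective RECIST progression (and death, for PFS), and say whether 11.45 events count in the main analysis.

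Cost: a short amendment, one extra analysis, and some off-treatment scans and visits for a limited number of patients. Footnote 1 already implies those scans. In the simulation, 8-weekly assessment throughout returns the null hazard ratio to 0.99 to 1.01.
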